**Table 6-17 QTc prolongations suspected to be related to capmatinib (Further guidance is provided in Section 6.3.2)**

Grade (CTCAE v5)	Mandatory dose modification
Grade 3 (Average QTcF ≥ 501 ms; >60ms change from baseline)	Interrupt capmatinib until resolved to grade ≤ 2, 
 
• If resolved ≤ 7 days, restart at the same dose level
 
• If not resolved within 7 days, restart at reduced dose level
 

Grade 4 (Torsades de pointes or polymorphic ventricular tachycardia or signs/symptoms of serious arrhythmia)	Permanently discontinue capmatinib

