## 6.3 Dose modifications

### 6.3.1 Mandatory dose modification and dose delay

For subjects who do not tolerate the protocol-specified dosing schedule, dose interruptions and/or reductions are mandated for treatment-related adverse events in order to manage subject safety and allow subjects to continue the study treatment.

Dose reductions are only allowed for capmatinib and ribociclib (refer to [Section 6.3.1.1](#)). Dose changes for spartalizumab, LAG525 and canakinumab are prohibited.

[Table 6-2](#) summarizes the mandatory dose modifications for specific treatment-related adverse events. If the specific adverse event is not listed, the guideline for ‘Other adverse events’ must be followed. AEs are to be graded according to NCI-CTCAE v5 ([ctep.cancer.gov](http://ctep.cancer.gov)) and all dose modifications should be based on the worst preceding toxicity. Deviations to mandatory dose interruptions and/or reductions are not allowed. Permanent treatment discontinuation is mandatory for specific events indicated as such in [Table 6-5](#) to [Table 6-37](#) and in [Section 6.3.1.5](#) or listed in [Section 7.1.5](#).

The investigator must follow the dose modifications for the study drug suspected to be related to the event:

- If the event is suspected to be related to spartalizumab, the investigator must follow the dose modifications specific for spartalizumab.
- If the event is suspected to be related to LAG525 or capmatinib or canakinumab or ribociclib, the investigator must follow the dose modifications specific for the suspected study drug.
- If it cannot be distinguished which of the study drugs within the combination is suspected to be related to the event, the investigator must follow the dose modifications specific to both study drugs within the combination.

Recommended management guidelines for suspected immune-related adverse events are provided in [Appendix 3](#) and can be amended according to the local or institutional guidelines.

Except for arm 1 where spartalizumab and LAG525 must be permanently discontinued at the same time, it is allowed for the other arms to discontinue one of the two study drugs within the combination. Permanent study treatment discontinuation is defined as the permanent discontinuation of both study drugs within the combination arm.

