### 6.3.1.1 Dose reductions

Dose reductions for spartalizumab, LAG525 and canakinumab are prohibited.

[figure not shown]
Dose reductions are only allowed for capmatinib and ribociclib. All dose reductions should be based on the worst preceding toxicity demonstrated at the last dose. Dose reduction must follow the dose reduction steps described in Table 6-3 for capmatinib and in Table 6-4 for ribociclib. For each subject, a maximum of 2 dose level modifications are allowed after which the subject must be discontinued from treatment with capmatinib/ribociclib (reduction below dose level -2 is not allowed: subjects on dose level -2 necessitating further dose reduction due to an adverse event must permanently discontinue capmatinib/ribociclib). Altering from BID dosing schedule for capmatinib is not allowed.

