**Table 6-3 Dose reduction steps for capmatinib**

Capmatinib dose levels	Capmatinib daily dose
Starting dose level	400 mg BID (= 2 x 200 mg tablets twice in a day; 800 mg total daily dose)
Dose level -1	300 mg BID (= 2 x 150 mg tablets twice in a day; 600 mg total daily dose)
Dose level -2	200 mg BID (= 1 x 200 mg tablets twice in a day; 400 mg total daily dose)

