### 6.3.2 Dose adjustments for QTcF prolongation suspected to be related to capmatinib

#### In case of QTcF >500 msec, (or QTcF prolongation >60 msec from baseline):

1. Assess the quality of the ECG recording and the QT value and repeat if needed
2. Interrupt capmatinib
3. Determine the serum electrolyte levels (in particular hypokalemia, hypomagnesemia). If abnormal, correct abnormalities before resuming capmatinib.
4. Review concomitant medication associated with QT prolongation, including drugs with a ‘Known’, ‘Possible’, or ‘Conditional’ risk of Torsades de Pointes” (refer to qtdrugs.org), and drugs with the potential to increase the risk of study drug exposure related QT prolongation
5. Check capmatinib dosing schedule and treatment compliance

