#### After confirming ECG reading at site, if QTcF > 500 msec

- Interrupt capmatinib
- Repeat ECG and confirm ECG diagnosis by a cardiologist or central ECG lab
- If QTcF confirmed > 500 msec:
  - Correct electrolytes, eliminate culprit concomitant treatments, and identify and address clinical conditions that could potentially prolong the QT interval.
  - Consult with a cardiologist (or qualified specialist)
  - Increase cardiac monitoring as indicated, until the QTcF returns to  $\leq 480$  msec.
- After resolution to  $\leq 480$  msec, consider re-introducing capmatinib at reduced dose, and increase ECG monitoring for the next cycle(s):
  - If QTcF remains  $\leq 500$  msec after dose reduction, continue planned ECG monitoring during subsequent treatment
  - If QTcF recurs > 500 msec after dose reduction, discontinue subject from capmatinib.

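### Capmatinib, confirmed QTcF above 500 msec that resolves within 7 days: Table 6-17 restarts at the same dose, Section 6.3.2 only at a reduced dose, and nothing says which prevails (minor)

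*Protocol*

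**What the plan says.** Table 6-17 (Section 6.3.1.4) defines the event as "Grade 3 (Average QTcF ≥ 501 ms; >60ms change from baseline". Capmatinib is interrupted until grade 2 or lower. The dose at restart then depends on time: "If resolved ≤ 7 days, restart at the same dose level", otherwise one level down. The column is headed as mandatory, and the table title refers the reader to Section 6.3.2.

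Section 6.3.2 has two blocks.
- The first opens "In case of QTcF >500 msec, (or QTcF prolongation >60 msec from baseline". It gives interruption and checks of the ECG, electrolytes, co-medication and dosing.
- The second is narrower: "After confirming ECG reading at site, if QTcF > 500 msec". It holds capmatinib until QTcF is 480 msec or less, and the site may then "consider re-introducing capmatinib at reduced dose, and increase ECG monitoring for the next cycle(s". If QTcF exceeds 500 msec again after the reduction, capmatinib is stopped.

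The second block has no 7-day branch and no same-dose option.

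Section 6.3.1 adds: "Deviations to mandatory dose interruptions and/or reductions are not allowed". Table 6-3 sets the steps at 800, 600 and 400 mg/day; level -1, for example, is "300 mg BID (= 2 x 150 mg tablets twice in a day; 600 mg total daily dose". Section 6.3.1.1 closes the scale at the bottom: "subjects on dose level -2 necessitating further dose reduction due to an adverse event must permanently discontinue capmatinib/ribociclib".

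**The concern.** A site with a confirmed QTcF above 500 msec that settles within a week finds two current instructions for the same event, and they give different doses. The looser one carries the mandatory label. The stricter one is where the table itself sends the reader. No sentence ranks them. What is at stake is the dose to which a subject returns shortly after a marked QT prolongation, and at the lowest dose level whether the subject returns to capmatinib at all. The rule to stop on recurrence after a reduction also appears only in Section 6.3.2.

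**Working it through.** The plan gives no figure to reproduce, so the check sets the two rules side by side.

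**Dose at restart, confirmed QTcF above 500 msec.** Doses are from Table 6-3.

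| Level at event | Table 6-17, resolved in 7 days or less | Section 6.3.2 | Difference |
|---|---|---|---|
| Starting | 800 mg/day | 600 mg/day | 1 - 600/800 = 25% lower |
| -1 | 600 mg/day | 400 mg/day | 1 - 400/600 = 33% lower |
| -2 | 400 mg/day | no lower level exists | restart against permanent discontinuation |

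Beyond 7 days both texts give a reduced dose, so the dose conflict is confined to events that resolve within 7 days. It also does not arise for an isolated change above 60 ms, because the second block of Section 6.3.2 covers only QTcF above 500 msec.

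**Limit for ending the hold.** Section 6.3.2 joins the two grade 3 conditions with 'or'. Reading Table 6-17 in the same way, with baseline b in ms:

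- Table 6-17 limit: L(b) = min(500, b + 60)
- Section 6.3.2 limit: 480
- Gap = L(b) - 480

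| Baseline (ms) | L(b) | Gap |
|---|---|---|
| 400 | 460 | -20 (table stricter) |
| 420 | 480 | 0 |
| 430 | 490 | +10 (table looser) |
| 440 | 500 | +20 |
| 460 | 500 | +20 |

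The limits differ at every baseline except 420 ms. The table is looser only above 420 ms and stricter below. Baselines above 420 ms can occur, because arm 2 excludes only a resting QTcF above 480 msec (Section 5.3.2, criterion 22).

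**Reach.** Arm 2 had 43 treated subjects at both Amendment 4 (24-Jan-2020) and Amendment 5 (26-Jun-2020), and its enrollment was already closed at Amendment 4. The interval is 7 + 29 + 31 + 30 + 31 + 26 = 154 days, or 22 weeks. The last scheduled arm 2 ECG before end of treatment is at C3D1 (Table 7-6), which is day 57. Any subject still on capmatinib at Amendment 5 is past it, so the event would now have to be found on an unscheduled ECG.

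**The case against.** The strongest reply is that a careful site is not trapped. Section 6.3.1 forbids departing from mandatory interruptions and reductions, and a same-dose restart is neither. Reducing the dose therefore breaches nothing, and Section 6.3.2 is the detailed procedure to which the table points. This stands: a reader might infer that the protocol compels same-dose restart, and it does not. It does not remove the conflict, because a site that restarts at the same dose also has direct support in the text. The word consider in Section 6.3.2 leaves open whether to re-introduce capmatinib, but it adds no same-dose option. Reserving the table's same-dose branch for an isolated change above 60 ms also fails, because the row names 501 ms expressly.

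A reader might also take the two hold limits as a second contradiction. They are a mismatch only: each sets a condition before restart, and waiting for the later one satisfies both.

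The dose contrast need not last. Section 6.2 allows return to the previous level after 4 weeks at the reduced dose without recurrence, if the subject is deriving benefit. That softens the first two rows of the dose table but not discontinuation at level -2.

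Finally, Section 1.2.3.2.3 reports no QT risk for capmatinib on available data, and arm 2 was dropped for futility. Both points limit reach and severity. Neither reconciles the two texts.

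**Conclusion.** The dose conflict is real and sits in current text: for a confirmed QTcF above 500 msec resolving within 7 days, the same subject restarts at the same dose under Table 6-17 and at a reduced dose, or not at all from level -2, under Section 6.3.2. The hold limits are a secondary mismatch of at most 20 ms in the looser direction. That figure rests on reading the two grade 3 conditions as alternatives, as Section 6.3.2 and the ribociclib Table 6-36 both do.

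Severity is minor. The arm is closed, and the number of subjects still on capmatinib is not stated and may be zero. A reader might infer some effect on the trial's conclusions, but alpha, power and endpoints are untouched. The correction is still worth making: it is small, and the looser of two QT safety rules is the one labelled mandatory.

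**What to change.** In the grade 3 row of Table 6-17, separate the two conditions.

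- **Confirmed QTcF of 501 ms or more:** hold capmatinib until QTcF is 480 ms or less and no longer more than 60 ms above baseline. Then restart only at a reduced dose level, with increased ECG monitoring; discontinue permanently if already at level -2. Discontinue permanently if QTcF above 500 ms recurs after the reduction.
- **Isolated change above 60 ms from baseline:** keep the existing 7-day rule.
- **Re-escalation:** state whether Section 6.2 applies after a confirmed QTcF above 500 ms. Otherwise the reduced dose can be reversed after 4 weeks without anyone having decided that it should be.

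Both hold conditions are needed. With a baseline of 400 ms, a QTcF of 470 ms is below 480 ms but 470 - 400 = 70 ms above baseline, which is still grade 3.

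The revised row would follow Section 6.3.2 and resemble the ribociclib rule in Table 6-36, which requires return below 481 ms, a one-level reduction, and discontinuation if 501 ms or more recurs.

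The cost is one table row and one sentence on re-escalation in a written amendment, with no change to data collection or analysis. There is a precedent: Amendment 4 added a capmatinib stopping rule for myocarditis and other cardiac events when arm 2 enrollment was already closed.

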**Table 6-18 Diarrhea, vomiting or nausea suspected to be related to capmatinib**

Grade (CTCAE v5)	Mandatory dose modification
Diarrhea	
Grade 2 (despite maximal anti-diarrheal medication)	Interrupt capmatinib until resolved to grade ≤ 1, then restart at same dose level 
 
• If diarrhea returns as grade ≥ 2, interrupt capmatinib until resolved grade ≤ 1, then restart at reduced dose level
 

Grade 3 or 4 (despite maximal anti-diarrheal medication)	Interrupt capmatinib until resolved to grade ≤ 1, then restart at reduced dose level
Vomiting	
Grade 2 (despite standard anti-emetics)	Interrupt capmatinib until resolved to grade ≤ 1, then restart at same dose level

Grade (CTCAE v5)	Mandatory dose modification
	If vomiting returns as grade $\geq 2$ , interrupt capmatinib until resolved to grade $\leq 1$ , then restart at reduced dose level
Grade 3 and 4 (despite standard anti-emetics)	Interrupt capmatinib until resolved to grade $\leq 1$ , then restart at reduced dose level
Nausea	
Grade 3 (despite standard anti-emetics)	Interrupt capmatinib until resolved to grade $\leq 1$ , then restart at reduced dose level

**Table 6-19 Skin events suspected to be related to capmatinib**

Grade (CTCAE v5)	Mandatory dose modification
Grade 3, despite skin toxicity therapy	Interrupt capmatinib until resolved to grade $\leq 1$ , 
 
• If resolved in <math>\leq 7</math> days, restart at reduced dose level
 
• If not resolved within 7 days (despite appropriate skin toxicity therapy), permanently discontinue capmatinib
 

Grade 4, despite skin toxicity therapy	Permanently discontinue capmatinib
* During the whole duration of treatment with capmatinib, the patient is recommended to use precautionary measures against ultraviolet exposure (e.g., use of sunscreen, protective clothing and avoid sunbathing or using a solarium extensively).	

**Table 6-20 Pneumonitis or interstitial lung disease (ILD) suspected to be related to capmatinib**

Grade (CTCAE v5)	Mandatory dose modification
Grade 1	Interrupt capmatinib during diagnostic workup for pneumonitis/ILD If ILD/pneumonitis is confirmed permanently discontinue capmatinib Restart at reduced dose level upon resolution 
 
• If pneumonitis does not resolve within 6 weeks, permanently discontinue capmatinib.
 
 2nd recurrence Interrupt capmatinib until resolved, then restart at reduced dose level. 
 
• If pneumonitis does not resolve within 6 weeks, permanently discontinue capmatinib.
 
 3rd recurrence Permanently discontinue capmatinib.
Grade 2	Interrupt capmatinib dose during diagnostic workup until improvement to $\leq$ grade 1. If ILD/pneumonitis is confirmed permanently discontinue capmatinib If ILD/pneumonitis is NOT confirmed: 
 
• if symptoms resolve to <math>\leq</math> grade 1 in <math>\leq 7</math> days, restart at reduced dose level
 
• If symptoms do not resolve within 7 days or recur after dose reduction, permanently discontinue capmatinib.
 

Grade 3 or 4	Permanently discontinue capmatinib

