#### **6.1.1.3 Capmatinib**

Capmatinib will be administered orally on a twice daily (BID) dosing schedule from Day 1 till Day 28 of each 28-day cycle. The starting dose of capmatinib will be 400 mg BID (total daily dose: 800 mg).

On days of co-administration of capmatinib with spartalizumab, subjects should be instructed to take the morning dose of capmatinib during the clinic visit, when instructed by site personnel. The sequence of administration of capmatinib and spartalizumab is left at the investigator's discretion.

Guidance on dose modification is provided in [Section 6.3](#). Please refer to [Section 6.3.1.2](#) for the maximum duration allowed for a dose interruption.

- Subjects should take capmatinib twice daily at approximately the same time each day in the morning and in the evening [REDACTED]. The morning and the evening doses should be taken 12 ( $\pm$  4) hours apart, although 12-hour interval is highly recommended. If a dose is not taken within 4 hours of the planned dosing time, the missed dose should not be replaced.
- Capmatinib can be administered with or without food. Each dose of capmatinib is to be taken with a glass of water (at least 8 ounces – approximately 250 mL) and consumed over as short a time as possible (i.e. not slower than 1 tablet every 2 minutes).
- Subjects should be instructed to swallow the tablets whole and not to chew them.
- Subjects should be instructed not to make up for missed doses or partial doses (i.e. when the entire dose is not taken as instructed). A missed or partial dose will be defined as a case when the full dose is not taken within 4 hours of the scheduled twice daily dosing. If that occurs, then the dose (or part remaining dose) should not be taken and dosing should restart with the next scheduled dose. If vomiting occurs, no attempt should be made to replace the vomited dose before the next scheduled dose. Subjects should be instructed to inform the investigational site staff of any missed or delayed doses.
- During the whole duration of treatment with capmatinib, precautionary measures should be taken against ultraviolet exposure (e.g. sunscreen, protective clothing, avoid sun exposure or solarium).

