Scheduled dosing of spartalizumab, LAG525 and canakinumab may, at the discretion of the investigator, be delayed by up to 4 days if subjects present with conditions that require withholding of dose. Outside of this 4 day window, the dose will be considered missed. After a dose is missed, every effort should be made to return to the original schedule of administration.

Please refer to [Section 6.3.1.2](#) for the maximum duration allowed for a dose interruption for each study drug.

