### 6.3.1.2 Maximum duration of study drug(s) interruption

If the treatment with spartalizumab is interrupted for more than 12 weeks (counted from the time the AE reaches a grade that leads to spartalizumab interruption), spartalizumab must be permanently discontinued.

If the treatment with LAG525 is interrupted for more than 12 weeks (counted from the time the AE reaches a grade that leads to LAG525 interruption), LAG525 must be permanently discontinued.

If the treatment with capmatinib is interrupted for more than 3 consecutive weeks (counting from the first day when a dose was interrupted), then capmatinib must be permanently discontinued.

If the treatment with ribociclib is interrupted for more than 28 consecutive days due to ribociclib-related toxicity (counting from the first day when a dose was interrupted, including the 7 days of planned interruption of dosing between Day 22-28 of a cycle), then ribociclib must be permanently discontinued.

If the treatment with canakinumab is interrupted for more than 4 weeks (counted from the intended day of the next scheduled dose), canakinumab must be permanently discontinued.

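### The grade 1 row of Table 6-20 tells sites to stop capmatinib for good if ILD/pneumonitis is confirmed and then to restart it, with no condition separating the two

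*Protocol*

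**What the plan says.** Table 6-20 (under Section 6.3.1.4) gives the mandatory capmatinib modifications for suspected pneumonitis or ILD.

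- **Grade 1.** Capmatinib is interrupted during the workup. The row then says: "If ILD/pneumonitis is confirmed permanently discontinue capmatinib Restart at reduced dose level upon resolution". It adds "If pneumonitis does not resolve within 6 weeks, permanently discontinue capmatinib", provides for interruption and another restart at a reduced dose at a second recurrence, repeats the 6-week line, and requires permanent discontinuation at a third recurrence.
- **Grade 2.** The same stop applies to a confirmed case, but the restart lines are introduced by "If ILD/pneumonitis is NOT confirmed".
- **Grades 3 and 4.** Permanent discontinuation.

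On the force of these rows, Section 6.3.1 states: "Permanent treatment discontinuation is mandatory for specific events indicated as such in" Tables 6-5 to 6-37. It also states: "Deviations to mandatory dose interruptions and/or reductions are not allowed".

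On the length of an interruption, Section 6.3.1.2 covers capmatinib treatment that is "interrupted for more than 3 consecutive weeks (counting from the first day when a dose was interrupted), then capmatinib must be permanently discontinued". It makes no exception for pneumonitis. Sections 6.1.1.3 and 6.3.1 both send the reader there, the latter "for the maximum duration allowed for a dose interruption for each study drug".

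**The concern.** A confirmed case cannot be both permanently taken off capmatinib and restarted on it. If the restart is meant only for cases where the workup rules out ILD or pneumonitis, the row does not say so, and its later lines point the other way because they speak of pneumonitis resolving and recurring in a subject who is still eligible for the drug. A site therefore cannot tell from the row which case the restart and recurrence lines cover.

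The 6-week figure adds a smaller risk. A site that reads only this row may believe that capmatinib can be withheld for longer than Section 6.3.1.2 permits.

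What is at stake is the safety of arm 2 subjects, through a mandatory instruction that is hard to follow. The primary endpoint, the interim rules and arm 1A are not involved.

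**Working it through.** The main check is a comparison of text.

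**1. Grade 1 against grade 2 in Table 6-20**

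| Step | Grade 1 row | Grade 2 row |
|---|---|---|
| During workup | Interrupt | Interrupt |
| ILD/pneumonitis confirmed | Stop permanently | Stop permanently |
| Condition before restart | None | "If ILD/pneumonitis is NOT confirmed" |
| Restart | Reduced dose, on resolution | Reduced dose, if symptoms settle to grade 1 or below within 7 days |
| What has to resolve | Pneumonitis | Symptoms |
| Later episodes | Second recurrence: restart again; third: stop | Recurrence after dose reduction: stop |

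The two rows run in parallel up to the confirmed case. The grade 1 row then lacks the line that makes the grade 2 row coherent.

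**2. Does supplying the condition mentally repair the row?** Only in part. With the restart limited to unconfirmed cases, the resolution and recurrence lines still refer to pneumonitis, which would just have been ruled out. They form a complete rechallenge scheme: restart reduced, restart reduced again, stop. That is two reductions, the maximum in Section 6.3.1.1, and Table 6-3 has two steps (400 to 300 to 200 mg BID). A rechallenge scheme for pneumonitis and a rule to stop when pneumonitis is confirmed cannot govern the same case. The row reads as if two schemes had been merged, although the Protocol does not say that this happened.

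**3. Which instruction prevails?** Section 6.3.1 makes a discontinuation indicated in the tables mandatory, so a confirmed case should be stopped. That leaves the restart and recurrence lines, which stand in the same mandatory column, without a stated case.

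**4. The two time limits**

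- Section 6.3.1.2: 3 × 7 = 21 days, counted from the first interrupted dose.
- Table 6-20, grade 1: 6 × 7 = 42 days; no starting point is given.

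Both are stop rules, so both can be obeyed, and Section 6.3.1.2 governs how long the drug may be off. If both clocks start at the first interrupted dose, the 21-day cap always acts first and the 6-week line adds nothing. If the 6 weeks run from onset of the event, the order reverses when onset precedes the interruption by more than 42 − 21 = 21 days. The 6-week line is thus redundant under one reading of its start and active under another.

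**5. Who is affected?** The Amendment 5 rationale counts 45 + 43 + 42 + 44 = 174 subjects treated in part 1, 43 of them in arm 2. The 43 are everyone ever dosed in that arm. The Protocol gives no count of those still on capmatinib.

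**The case against.** The strongest reply is that the stop is conditional and comes first. Read in order, the row means: interrupt for workup, stop if confirmed, otherwise restart. The safe action in a confirmed case is then clear, and Section 6.3.1 backs it. This stands as far as it goes, and it is why the point is minor. It does not explain the restart and recurrence lines, which name pneumonitis.

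A line may have been lost in reproducing the table, since the row moves to a second recurrence with no heading for the first episode. This cannot be excluded, but the matching condition survives in the next row of the same table, which makes it unlikely.

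On the time limits, a reader might infer that 6 weeks and 3 weeks contradict each other, or that the 6-week line can never act. The documents support neither. Both are stop rules and can be followed together; one times resolution of an event and the other times drug interruption; and Table 6-20 gives no start for its 6 weeks. Two sections also direct sites to the cap. What remains is a figure in the row that exceeds the governing limit and may mislead.

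Finally, arm 2 was declared futile at interim analysis 1 and its enrolment stopped (Section 4.1.1), so the point may be moot in practice. Section 4.1.3 keeps subjects on treatment until progression or another listed reason, and Amendment 4 added a capmatinib stopping rule to Table 6-23 in the same amendment that recorded the arm's closure. This shows that the capmatinib rules were still being maintained. It does not show that anyone was still taking the drug.

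**Conclusion.** The point holds. The grade 1 row of Table 6-20 is self-contradictory as a mandatory safety instruction, because the condition that separates stop from restart is missing and the later lines describe rechallenge in pneumonitis. The mismatch between 6 weeks and the 3-week cap is secondary and is a matter of consistency.

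The size is small: one table row, relevant only to arm 2 subjects still on capmatinib who have suspected grade 1 ILD or pneumonitis. A reader might take the 43 subjects treated in arm 2 as the number exposed, or infer that confirmed cases have been restarted. The Protocol supports neither. The 43 counts everyone dosed, the number still on drug is unstated and may be zero, and no such restart is reported. No efficacy analysis, interim rule or arm 1A decision changes.

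The conclusion assumes that the row is printed in full.

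**What to change.** 1. In the grade 1 row, insert the grade 2 condition, "If ILD/pneumonitis is NOT confirmed", directly before the restart instruction.
2. Reword the resolution and recurrence lines to refer to the suspected findings. They should not say pneumonitis, which is ruled out in that branch. They should not say symptoms either, because the Protocol treats grade 1 as asymptomatic (Tables 6-37 and 14-14), so a rule that waits for symptoms to clear could not be applied.
3. In both places, replace the 6 weeks with 3 weeks, or refer to Section 6.3.1.2.

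If the sponsor does intend rechallenge after confirmed grade 1 pneumonitis, the opposite edit is needed: delete the stop for confirmed cases from the grade 1 row and write any longer interruption into Section 6.3.1.2 as an explicit exception.

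Either way this is a wording change, by investigator letter or in the next amendment. It changes no data collection and no analysis.
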